### 8.1. Analysis variables

The analysis variables consist of baseline participant characteristic, safety, and laboratory measurements for primary- and secondary-objective analyses.

### 8.2. Analysis tools

Analyses for primary endpoints will be performed in SAS. All other descriptive and inferential statistical analyses will be performed using SAS, StatXact, S-Plus, and/or R statistical software.

### 8.3. Baseline comparability

Treatment arms will be compared for baseline participant characteristics using descriptive statistics.

### 8.4. Safety/tolerability analysis

All participants who received at least 1 partial or complete infusion will provide some safety data.

#### 8.4.1. Reactogenicity

The number and percentage of participants experiencing each type of reactogenicity sign or symptom will be tabulated by severity and treatment arm and the percentages displayed graphically by arm. For a given sign or symptom, each participant's reactogenicity will be counted once under the maximum severity for all infusion visits. In addition, to the individual types of events, the maximum severity of local pain or tenderness, induration or erythema, and of systemic symptoms will be calculated.

#### 8.4.2. AEs and SAEs

AEs will be summarized using MedDRA System Organ Class and preferred terms. Tables will show by treatment arm the number and percentage of participants experiencing an AE within a System Organ Class or within preferred term category by severity or by relationship to study product or mucosal sampling. For the calculations in these tables, a participant with multiple AEs within a category will be counted once under the maximum severity or the strongest recorded causal relationship to study product or mucosal sampling. Formal statistical testing comparing arms is not planned since interpretation of differences must rely heavily upon clinical judgment.

A listing of SAEs reported to the DAIDS Regulatory Support Center (RSC) Safety Office will provide details of the events including severity, relationship to study product or mucosal sampling, time between onset and last infusion, and number of infusions received.

#### 8.4.3. Local laboratory values

Boxplots of local laboratory values will be generated for baseline values and for values measured during the course of the study by treatment arm and visit. Each boxplot will show the first quartile, the median, and the third quartile. Outliers (values outside the boxplot) will also be plotted. If appropriate, horizontal lines representing boundaries for abnormal values will be plotted.

For each local laboratory measure, summary statistics will be presented by treatment arm and time point, as well as changes from baseline for post-enrollment values. In addition, the number (percentage) of participants with local laboratory values recorded as meeting Grade 1 AE criteria or above as specified in the DAIDS AE Grading Table (see Section 11.2 of the protocol) will be tabulated by treatment arm for each postinfusion time point. Reportable clinical laboratory abnormalities without an associated clinical diagnosis will also be included in the tabulation of AEs described above.

#### **8.4.4. Reasons for discontinuation of study product administration and early study termination**

The number and percentage of participants who discontinue study product administration and who terminate the study early will be tabulated by reason and treatment arm.

### **8.5. Analyses of mAb concentration and functional responses**

#### **8.5.1. General approach**

For the statistical analysis of lab endpoints, data from enrolled participants will be used according to the initial randomization assignment regardless of how many infusions they received. Additional analyses may be performed, limited to participants who received all scheduled infusions per protocol. Assay results that are unreliable, or from HIV-infected participants postinfection will be excluded. Since the exact date of HIV infection is unknown, any assay data from blood draws 4 weeks prior to an infected participant's last seronegative sample and thereafter may be excluded. If an HIV-infected participant does not have a seronegative sample postenrollment, then all data from that participant may be excluded from the analysis. Assay results that are from specimens collected outside of the visit window are generally also excluded unless otherwise noted in analyses (e.g., population pharmacokinetics analyses of concentrations over time) that account for the actual date of specimen collection.

For continuous assay data (eg, serum concentration of VRC01), graphical and tabular summaries of the distributions by treatment arm and timepoint will be made. Scatterplot matrix with correlation coefficient information between each pair of serum and mucosa drug levels at different timepoints will be provided. An appropriate data transformation (eg, log transformation) may be applied prior to testing to better satisfy analysis assumptions. Inference from these analyses would be limited by the small sample sizes of the groups.

For qualitative assay variables (eg, positive or negative), the analyses will be performed by tabulating the frequency of positive responses for each assay by group at each timepoint at which an assessment is performed. Crude response rates will be presented with their corresponding 95% confidence interval estimates calculated using the score test method [66].

More sophisticated analyses of drug-level data and other assay data collected over time employing repeated measures methodology that is valid under the missing at random (MAR) assumption (for example, nonlinear mixed effects models) may be utilized to incorporate outcome responses over several timepoints and to account for subject heterogeneity. MAR assumes that the probability of an observation being missing may depend upon the observed responses and upon observed covariates, but not upon any unobserved data. Generalized nonlinear models for response rates will use a binomial error distribution and for quantitative endpoints, a normal error distribution. All models will include as covariates all available baseline predictors of the missing outcomes.

In addition, non-compartment PK analysis will be performed to estimate PK parameters from individual time-concentration curves. The correlation between individual-level PK parameters estimated for different specimen types (serum vs. mucosa) may also be assessed. All statistical tests will be 2-sided and will be considered statistically significant if  $p \leq 0.05$ .

For the analysis of correlation between two continuous assay variables over time, graphical summary and tabular summary of the sample correlation at each given timepoint will be made. Cross-correlation of the 2 variables with different time lags may also be calculated and visually displayed if there are at least 10 participants with no missing data over time from both variables. Nonlinear or linear mixed effects models may also be used to predict mucosal drug levels based on serum drug levels collected at the same or previous timepoints.

For each tissue biopsy type, graphical and tabular summaries of the distributions of *ex vivo* inhibition of HIV-1 infectivity summarized by AUC (or other measurements) will be made for each challenge virus, treatment arm, and timepoint. Comparisons between groups 1-3 will be stratified by site. The difference between treatment arms at a specific timepoint will be tested with an extension of the nonparametric Wilcoxon rank sum test for two-way analysis (i.e., the Van Elteren test) if the data are not normally distributed and with a stratified 2-sample t-test if the data appear to be normally distributed. An appropriate data transformation may be applied to better satisfy assumptions of symmetry and homoscedasticity (constant variance). The same testing

approaches will be used to compare infectivity between male rectal vs. female cervical/vaginal, between male rectal vs. female rectal, and between female cervical vs. female vaginal at each time-point, stratified by dose groups.

### **ELISA for Hemoglobin**

Any secretion sample (semen, PriCol or Softcup) with extrapolated concentrations higher than 10,000 ng/ml are considered blood contaminated and excluded from any statistical analysis. These exclusions are identified by the lab investigator(s).

### **ELISA for IgG concentration and Quant-iT for Protein concentration**

Total protein concentration and total IgG concentration will be used for normalization of VRC01/LS concentrations in serum, secretions and tissues. Total protein and IgG concentrations in study samples will be calibrated via a five-parameter logistic (5PL) model of the standard samples on the same plate. The estimation of the standard curve and the calibration of study samples will be carried out using the nCal package in R (Fong et al., Biometrics, 2012; Fong et al., Bioinformatics, 2013). IgG- and protein-normalizations will be performed by dividing VRC01/VRC01LS levels (pg/mL) by the total IgG and protein concentrations (ng/mL), respectively.

The reported mAb concentrations reflect the measured concentration of mAb in the processed mucosal samples; and the reported values have accounted for the dilution factor in the assay but not the dilution factor due to sample processing and collection, which cannot be determined. Thus, these concentrations cannot be considered physiological concentrations within secretions or tissues.

### **Singulex assay for mucosal VRC01/VRC01LS Levels**

VRC01/LS concentrations will be calibrated via a 5PL model of the standard samples on the same plate. The machine Erenna detects single molecules of VRC01/VRC01LS as photons over a read time. Each measurement of photons above a threshold is considered a detected event and the sum of all photons from these events over the read time (i.e. signal intensity) is called the event photon (EP) measurement for the sample or standard. The EP curve of the VRC01/LS standard will be used to calibrate the VRC01/VRC01LS concentrations in mucosal and serum samples. The lower limit of quantitation (LLoQ) of each run is defined by the lowest standard maintaining less than or equal to 20% coefficient of variation (CV). The estimation of the standard curve and the calibration of study samples will be carried out using the nCal package in R (Fong et al., Biometrics, 2012; Fong et al., Bioinformatics, 2013).

Graphical and tabular summaries of the distributions of VRC01/LS mucosal levels normalized by total IgG/protein, as well as levels data without normalization will be made for each biopsy type, treatment arm, and time point. Correlation plots will be generated between different sample types.

### **ELISA for VRC01/VRC01LS Levels in Serum**

Concentration values below the limit of quantification ( $=1.0$  ug/ml) will be replaced by  $0.5$  ug/ml in all calculations. Spaghetti plots will be used to display each participant's time-concentration curves, with the treatment group geometric mean or median overlaid. The geometric mean as well as the median and inter-quartile ranges will be used to summarize the drug level at each time-point by treatment group in a summary table.

Individual-level non-compartmental pharmacokinetics (PK) analysis will be performed. Specifically, for Groups 1-3, we will compute drug accumulation based on the ratio of observed trough drug level measurements and the area under the observed time-concentration curve (AUC) for each participant, after the second, third and fourth (Groups 1 & 2 only) infusions as compared to the first. We will report the mean, median, and standard deviation (SD), in addition to the listing of individual values. AUC will be calculated based on raw (not log-transformed) data using the linear trapezoidal method. The actual visit dates will be used in these AUC calculations.

Lastly, for each participant in Groups 1-5, the terminal elimination rate and half-life will be calculated based on the log-linear portion of the time-concentration curve after the last infusion. The terminal rate (slope) will be determined by fitting a linear regression line over the log-transformed concentrations over the actual visit date (in days). The half-life is estimated as  $\log(2)$  divided by the terminal slope. The effect of participants' characteristics on various PK parameters and inter-individual variabilities of these parameters will be modeled via population compartmental pharmacokinetics analysis and reported separately.

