### 3. OBJECTIVES AND ENDPOINTS

#### 3.1. Primary objective:

*Primary objective 1:*

- To evaluate the safety and tolerability of VRC01/VRC01LS mAb administered through IV infusion.

*Primary endpoints 1:*

- Local and systemic reactogenicity, laboratory measures of safety, AEs, SAEs, and rates of discontinuation.

*Primary objective 2:*

- For each sex at birth, to evaluate the pharmacokinetics of VRC01 in serum versus mucosa in each mucosal compartment.

*Primary endpoint 2 (Groups 1 & 2 & 4):*

- Serum concentration of VRC01 out to Month 6 after the last infusion.
- Levels of VRC01 in genital and rectal secretions, as well as cervical, vaginal, and rectal tissues at the collection timepoints.

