### 10.3. Serum VRC01/LS Levels by ELISA

#### 10.3.1. List of Tables

- Summary statistics (i.e., N, N> LLoQ, geometric mean, median, min, max and IQR) of VRC01/LS concentration by visit (number and label), and treatment arm in all participants
- Summary statistics (i.e., N, N> LLoQ, geometric mean, median, min, max and IQR) of VRC01/LS concentration by visit (number and label), and treatment arm among participants who received all infusions
- Summary statistics (N, median and mean +/- SD) of the estimated half-life by treatment group among all participants.
- For Groups 1-3, summary statistics (N, geometric mean, median) of second vs. first, third/first, fourth vs first (if applicable) accumulation in terms of observed trough and observed AUC by treatment group among participants who received all infusions.

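### The serum accumulation ratios in SAP 8.5.2 and 10.3.1 ask for data the draw schedule does not provide, and the half-life fit is not exempted from the 0.5 ug/mL substitution

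*SAP*

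**What the plan says.** The serum ELISA part of SAP 8.5.2 plans individual non-compartmental summaries for Groups 1-3: ratios of observed troughs and of AUC under the observed curve "after the second, third and fourth (Groups 1 & 2 only) infusions as compared to the first". On the AUC it states "AUC will be calculated based on raw (not log-transformed) data using the linear trapezoidal method", with actual visit dates. It gives no rule for the concentration at time zero and no end point for the last interval. SAP 10.3.1 lists the matching table, including "fourth vs first (if applicable) accumulation in terms of observed trough and observed AUC by treatment group".

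In the same part of 8.5.2, results under 1.0 ug/mL are set to 0.5 "ug/ml in all calculations". Half-life comes from a regression of log concentration on time over "the log-linear portion of the time-concentration curve after the last infusion". That portion is not defined, and the fit is not exempted from the substitution.

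Covariate effects on the PK parameters "will be modeled via population compartmental pharmacokinetics analysis and reported separately". The primary PK endpoint for serum is "Serum concentration of VRC01 out to Month 6 after the last infusion".

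**The concern.** An accumulation ratio is informative only if numerator and denominator are measured the same way. In Groups 1-2 the draws after infusions 3 and 4 differ from those after infusion 1. One planned ratio cannot be filled at all, and others would reflect the sampling days as much as the drug. A reader of the third/first AUC table could conclude that exposure falls with repeat dosing.

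The substitution rule raises a separate problem. Putting 0.5 in place of a true value of a few hundredths flattens the fitted slope and lengthens the half-life. It does so by different amounts in groups that reach the quantification limit at different visits. Groups with the same elimination could then appear to differ.

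**Working it through.** **Which draws exist.** The serum storage row of Appendix H is shifted by text extraction, so I checked it against its own total. One draw of 76.5 mL (Visit 2), nine of 51 mL (Visits 4, 5, 7, 9, 12, 14-17) and three of 8.5 mL (Visits 6, 11, 13) give 76.5 + 9×51 + 3×8.5 = 561 mL. That is the stated total, and the visit-total row agrees. Footnote y says this serum covers the drug-level assay. For Groups 1-2:

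| Infusion | Day | Draws, days since that infusion | Day-56 draw |
|---|---|---|---|
| 1 | 0 | 1-15, 29-43, 56 | D56 |
| 2 | 56 | 1-15, 29-43, 56 | D112 |
| 3 | 112 | 15-29, 56 | D168 |
| 4 | 168 | 1-15, 29-43, 85-99, 183-197 | none (D224) |

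**Trough.** Nothing is drawn between D211 and D253. Protocol 9.4 ties trough samples to infusion visits, and none follows the fourth. Three troughs give two ratios; the plan asks for three.

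**AUC, Groups 1-2.** Assume mono-exponential decline with superposition, C(t) = Σ 2^(−(t−d)/h) over infusion days d. The half-life h is 15 days (protocol 4.7.1.2), with 12-18 tried. Blood at infusion visits is taken before the dose (Appendix L, footnote i). The true third/first ratio is 1 + 2^(−56/15) + 2^(−112/15) = 1.08.

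Mid-window, starting from the pre-dose value, in units of the first peak:

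- Interval 1: 8×(0+0.691)/2 + 28×(0.691+0.189)/2 + 20×(0.189+0.0752)/2 = 17.74
- Interval 3: 22×(0.0808+0.391)/2 + 34×(0.391+0.0813)/2 = 13.22
- Ratio: 13.22/17.74 = 0.75

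| Time-zero rule | Third/first, early to late window | Geometric mean, visit days uniform in window |
|---|---|---|
| Pre-dose value | 0.73-0.79 | 0.74 |
| First sample onward | 0.48-0.59 | 0.53 |
| Back-extrapolated log-linearly | 1.10-1.15 | 1.11 |

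For h of 12-18 days, the pre-dose rule gives 0.60-0.87 against a true 1.04-1.13. Second/first is 1.08-1.12 under all three rules at 15 days, so the trapezoid itself is not the cause.

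Fourth/first (pre-dose start, mid-window, true 1.08) is 0.94, 1.29 or 1.33 if it ends at Visit 15, 16 or 17. Cut at day 56 by log-linear interpolation between Visits 15 and 16, it is 1.10.

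**Group 3.** Infusions are at days 0, 84 and 168, and the second interval has only days 15-29 and 84. No human VRC01LS half-life is given, so I assumed 37.5-45 days (2.5-3 times 15, from the macaque ratios in protocol 4.6.2). Second/first AUC is then 1.10-1.18 against a true 1.21-1.27. The nearest sample to the third trough is Visit 16, 1-15 days late: 0.95-1.33 against 1.26-1.35.

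**Half-life.** Day-56 troughs come from HVTN 104 (protocol 4.7.1.3): 4.1 ug/mL at 10 mg/kg and 10.4 at 30 mg/kg. For Groups 1-2 they are multiplied by the four-infusion accumulation factor, 1.08 at 15 days. Then C(t) = trough × 2^((56−t)/h), and half-life = ln 2/|slope| from least squares on ln C. Mid-window at a true 15 days:

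| Group | Concentrations, ug/mL | Set to 0.5 | Slope per day | Fitted half-life (early-late window) |
|---|---|---|---|---|
| 1 | 40.7, 11.2, 0.84, 0.009 | last two | −0.0240 | 28.9 d (27.1-31.5) |
| 2 | 103.3, 28.3, 2.13, 0.023 | last one | −0.0289 | 23.9 d (22.5-25.5) |
| 4 | 95.6, 26.2, 7.19, 1.97, 0.283, 0.041 | last two | −0.0331 | 21.0 d (19.6-22.5) |

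Mid-window at a true 12 days the fits are 26.2, 21.9 and 19.3; at 18 days, 31.4, 25.4 and 22.2. Quantifiable points alone return the true value, from 2, 3 and 4 points at 15 days.

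**The case against.** The strongest reply has five parts.

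- **The fourth AUC needs only an end point.** Interval 4 has the same two early draws as interval 1, and cutting it at day 56 gives 1.10, as good as second/first. This stands: interval 4 needs a stated rule, whereas interval 3 lacks a sample.
- **An observed curve would not be back-extrapolated.** This also stands, and it makes 0.73-0.79 the likelier printed result. That is the misleading one.
- **An analyst confined to the log-linear portion would drop substituted values.** Possibly. In Group 1 they form a flat pair. In Group 2 only one value is replaced, and it shows as a last-segment half-life of 98×ln 2/ln(2.13/0.5) ≈ 47 days after two segments of 15. A careful analyst would see the break, but the written rule points toward keeping the value. The half-life figures are therefore a worst case.
- **The curves are noise-free and one-compartment.** Recovery of 15 days from quantifiable points is then automatic. Table 4-9 shows 28-day trough ratios of 57/35 = 1.63 and 89/57 = 1.56, against 1 + 2^(−28/15) = 1.27 from this model. The sizes are illustrations; the schedule gaps do not depend on them. Operative visit windows are in the Study Specific Procedures, which I did not have; I used the appendix day ranges.
- **The summaries are descriptive, with individual values listed and population PK already planned.** True. This limits the consequence and makes the repair cheap. It does not make the planned tables correct.

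**Conclusion.** The concern holds. That the fourth/first trough in Groups 1-2 has no observations follows from the schedule alone. So does the mismatch of the third AUC interval, and of the fourth unless an end point is set. The size of the distortion is model-based: assuming a 15-day half-life and mono-exponential superposition, third/first AUC reads 0.73-0.79 when the truth is 1.08. Group 3's second interval has a milder version. If the 0.5 rule is carried into the slope fit, VRC01 half-life is overstated 1.4 to 1.9 times (21.0/15 to 28.9/15), with false differences between Groups 1, 2 and 4.

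Second/first trough and AUC, and third/first trough, are sound in Groups 1-2. No test on the ratios is planned and the primary concentration endpoints are not affected. It should still be corrected before the final analysis, because following the text as written gives wrong descriptive PK in support of primary objective 2.

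**What to change.** In SAP 8.5.2 and 10.3.1:

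- Delete the observed fourth/first trough ratio.
- Replace the observed AUC ratios for intervals 3 and 4 (Group 3: interval 2) with AUC over a common dosing interval from the planned population PK model. Alternatively, keep them labelled as not comparable with interval 1, and state the time-zero rule and end point used. Group 3's third interval also needs an end point.
- Label Group 3's third trough with its actual day.
- Limit the 0.5 substitution to the concentration summaries, and leave values below the quantification limit out of the terminal-slope fit.
- Report the number of quantifiable points per participant and the number of participants estimable per group.
- For Group 1, make the population PK half-life the main estimate, treating values below the limit as left-censored.

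The cost is SAP wording only: no visit or sample changes, and SAP 8.5.1 already foresees "population pharmacokinetics analyses of concentrations over time". Some Group 1 non-compartmental half-lives will rest on two points and be imprecise.

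I would not add a three-point minimum. It would keep about 38-40% of Group 1 and move the median half-life from 15.0 to 16.1-16.9 days by selecting slow eliminators. That assumes a half-life CV of 10-14% and a log-SD of 0.37-0.42 for the day-56 trough, reading the HVTN 104 range of 3.1-5.3 as a 95% interval from 10-12 people.
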